12. ADVERSE EVENT REPORTING

12.1. Study Disease

Deterioration of the subject's condition due to multiple myeloma and signs and symptoms that, according to the investigator, are expected and well known consequences of multiple myeloma, both in intensity and frequency should not be reported as AEs or SAEs.

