1.1. Background

1.1.1. Multiple Myeloma

Multiple myeloma is a plasma cell disorder, characterized by uncontrolled, malignant proliferation and accumulation of plasma cells. In the majority of patients, the malignant plasma cells produce a monoclonal protein (M protein or paraprotein). The majority of M proteins are immunoglobulin (Ig) G ($\sim 50\%$) and IgA ($\sim 20\%$). The proliferation of myeloma cells causes displacement of the normal bone marrow. Myeloma cells are highly dependent upon external factors, ie, the microenvironment in bone marrow, including stromal cells and cytokines (eg, interleukin [IL]-6) (Klein 1989, Vidriales 1996). In multiple myeloma, the major clinical findings include anemia, monoclonal Ig (M protein) in serum and/or urine, abnormal bone radiographs (bone resorption seen as diffuse osteoporosis or characteristic lytic lesions), hypercalcemia, renal insufficiency or failure, and neurologic complications.

Multiple myeloma accounts for approximately 1% of all malignancies and 10% of all hematologic malignancies, with a higher frequency in African Americans where it accounts for 20% of all hematologic malignancies (Howe 2001). In the United States (US), approximately 11,000 deaths each year are related to multiple myeloma, and the estimated number of new cases has risen from 15,270 in 2004 to 20,180 in 2010. At present, there is no cure available.

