9.3. Endpoints

The primary endpoint for this study will be the incidence of AEs.

The secondary endpoints are:

- The rate of response according to the International Uniform Response Criteria (Rajkumar 2011) ²¹
- PK variables (AUC, C_{max} , minimum or trough concentration in serum [C_{min}], time to C_{max} [T_{max}], apparent clearance [CL], volume of distribution [V], and elimination half-life [$t_{1/2}$])
- Time to progression
- Duration of response
- Progression-free survival (PFS)

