12.2. Pre-existing Conditions

In this study, a pre-existing condition (ie, a disorder that was present before the AE reporting period started and noted in the medical history or physical examination eCRF) should not be reported as an AE. If a pre-existing condition worsens during the Treatment Period, the event should then be reported as an AE.

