12.4. Definitions

12.4.1. Adverse Event Definitions and Classifications

Adverse Event

An AE is any untoward medical occurrence in a clinical study subject administered a medicinal (investigational or non-investigational) product. An AE does not necessarily have a causal relationship with the treatment. An AE can therefore be any unfavorable and unintended sign (including an abnormal finding), symptom, or disease temporally associated with the use of a medicinal (investigational or non-investigational) product, whether or not related to that medicinal (investigational or non-investigational) product. (Definition per International Conference on Harmonisation [ICH])

This includes any occurrence that is new in onset or aggravated in severity or frequency from the baseline condition, or abnormal results of diagnostic procedures, including laboratory test abnormalities.

Note: The sponsor collects adverse events starting with the signing of the ICF (refer to Section 12.6.1, All Adverse Events, for time of last adverse event recording).

Serious Adverse Event

A serious adverse event based on ICH and EU Guidelines on Pharmacovigilance for Medicinal Products for Human Use is any untoward medical occurrence that at any dose:

- Results in death
- Is life-threatening (The subject was at risk of death at the time of the event. It does not refer to an event that hypothetically might have caused death if it were more severe.)
- Requires inpatient hospitalization or prolongation of existing hospitalization
- Results in persistent or significant disability/incapacity
- Is a congenital anomaly/birth defect
- Is a suspected transmission of any infectious agent via a medicinal product
- Is Medically Important*

*Medical and scientific judgment should be exercised in deciding whether expedited reporting is also appropriate in other situations, such as important medical events that may not be immediately life threatening or result in death or hospitalization but may jeopardize the subject or may require intervention to prevent one of the other outcomes listed in the definition above. These should usually be considered serious.

Unlisted (Unexpected) Adverse Event/Reference Safety Information

An adverse event is considered unlisted if the nature or severity is not consistent with the applicable product reference safety information. For daratumumab, the expectedness of an adverse event will be determined by whether or not it is listed in the Investigator's Brochure.

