12.6.1. All Adverse Events

The investigator must report all directly observed AEs and all AEs reported by the subject, whether spontaneously or in response to general, nondirected questioning (eg, "How has your health been since the last visit?"). For each AE reported by the subject, the investigator should obtain all the information required to complete the AE page of the eCRF, in accordance with the guidelines that accompany it.

All adverse events and special reporting situations, whether serious or non-serious, will be reported from the time a signed and dated ICF is obtained until 30 days after the last dose of any component of the treatment regimen. As of Amendment 7, only SAEs will be collected (see Table 3 and Attachment 8). Nonserious medical events (signs, symptoms, diagnosis) that occur between the Screening Visit or before the first infusion and the first study drug treatment at Cycle 1 Visit 1 should be documented in the medical history. All AEs that occur in subjects during the AE reporting period must be reported, whether or not the event is treatment related.

Serious adverse events, including those spontaneously reported to the investigator within 30 days of the last dose of any component of the treatment regimen, must be reported using the Serious Adverse Event Form. The sponsor will evaluate any safety information that is spontaneously reported by an investigator beyond the time frame specified in the protocol.

All adverse events, regardless of seriousness, severity, or presumed relationship to study drug, must be recorded using medical terminology in the source document and the CRF. Whenever possible, diagnoses should be given when signs and symptoms are due to a common etiology (eg, cough, runny nose, sneezing, sore throat, and head congestion should be reported as "upper respiratory infection"). Investigators must record in the CRF their opinion concerning the relationship of the adverse event to study therapy. All measures required for adverse event management must be recorded in the source document and reported according to sponsor instructions.

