Disease progression should not be submitted as serious adverse event term. Instead, signs and symptoms of clinical sequelae resulting from disease progression/lack of efficacy will be reported if they fulfill the serious adverse event definition (refer to Section 12.4.1, Adverse Event Definitions and Classifications).

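### Sections 12.1 and 12.6.2 of the protocol give opposite instructions on reporting serious consequences of myeloma, in a trial whose primary endpoint is AE incidence

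*Protocol*

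**What the plan says.** Protocol Section 12.1 (Study Disease) has two limbs. It starts with "Deterioration of the subject's condition due to multiple myeloma and signs and symptoms that, according to the investigator" and ends by saying that such "expected and well known consequences of multiple myeloma, both in intensity and frequency should not be reported as AEs or SAEs". Deterioration due to the disease is the first limb. Signs and symptoms that the investigator considers expected are the second. Both are taken out of AE and SAE reporting.

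Section 12.6.2 (Serious Adverse Events) says that disease progression is not to be used as an SAE term, but that "signs and symptoms of clinical sequelae resulting from disease progression/lack of efficacy will be reported if they fulfill the serious adverse event definition". It also makes any event requiring hospitalization an SAE apart from three listed exceptions: overnight observation after a daratumumab infusion, admissions not meant to treat an acute illness or AE, and procedures planned before entry. Admission for the study disease is not among them.

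The general rules are wider still:
- Section 12.2: "If a pre-existing condition worsens during the Treatment Period, the event should then be reported as an AE".
- Section 12.4.1 counts as an AE any occurrence that is "new in onset or aggravated in severity or frequency from the baseline condition".
- Section 12.6.1: "All adverse events, regardless of seriousness, severity, or presumed relationship to study drug, must be recorded".

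None of these sections refers to 12.1 or makes an exception for it. Section 9.3 states: "The primary endpoint for this study will be the incidence of AEs".

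**The concern.** The protocol's own description of myeloma (Section 1.1.1) lists anemia and "hypercalcemia, renal insufficiency or failure, and neurologic complications" among the main clinical findings. Some of these can also be toxicity. Section 6.5 reports free hemoglobin during daratumumab infusions and names hemolysis above Grade 3 as a DLT. Section 1.1.4 reports daratumumab binding in the kidney. Section 12.1 asks the investigator to decide that an event is the myeloma before any record exists, in an open study with no concurrent control. Sections 11.11 of the protocol and 6.1 of the SAP analyze reported, treatment-emergent events only, so an event withheld at that step does not enter the primary endpoint.

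For serious events the stake is current. Since Amendment 7 only SAEs are collected (Section 12.6.1), laboratory tests are local and follow institutional practice (9.2.2), and the IDMC stops reviewing safety after the primary analysis (11.13). Under Amendment 8 collection is limited to SAEs and second primary malignancies (9.2, 12.6). Monitors are asked to check that SAEs are adequately reported (17.8), against two rules that disagree.

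**Working it through.** There is no stated figure to reproduce. The check sets the sections side by side.

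**Step 1: a serious event.** Take a subject whose myeloma is progressing and who is admitted for hypercalcemia that the investigator attributes solely to the plasma cell disorder, which is a progression criterion in Attachment 5.
- Under 12.1 this is deterioration due to myeloma, so it is reported neither as an AE nor as an SAE.
- Under 12.6.2 it is a sign of progression that meets the SAE definition by hospitalization, so it is reported. No hospitalization exception applies.

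One might try to harmonize the two by saying that 12.1 covers only what is expected in intensity and frequency, and 12.6.2 covers the rest. On the sentence as written, that qualifier attaches to signs and symptoms and not to the first limb, deterioration due to the disease. The sequelae of progression fall under that first limb. The conflict remains, and whichever section a site follows, it breaches the other.

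**Step 2: a non-serious event.** Sections 12.1 to 12.3 stand together as rules on what is not an AE. The study disease has its own rule in 12.1. Section 12.2 concerns disorders noted in the medical history or physical examination eCRF. The sentence in 12.6.1 speaks of relationship to study drug, which is a different question from whether an occurrence is the study disease. Reading 12.1 as a specific exception is possible, although no text says so. This is tension, not a direct contradiction.

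**Step 3: what a second route would catch.** SAP 6.3 tabulates laboratory toxicity grades and shifts from baseline independently of AE records. The IDMC received laboratory data after each cohort's first cycle (11.13). Clinical signs have no such route: SAP 6.4 says post-baseline physical examination findings were collected as AEs and are not summarized.

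**Step 4: sensitivity, on assumed values only.** Let N = 30 (Phase 2, Section 11.2), p be the true share of subjects with some clinical event, and w the share of those subjects whose event is withheld. Then q = p(1 − w), the expected number reported is Nq, and P(at least 2 reported) = 1 − (1 − q)^N − Nq(1 − q)^(N−1).

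| Assumed p | w = 0 | w = 0.10 | w = 0.25 | w = 0.50 |
|---|---|---|---|---|
| 0.20: expected reported | 6.0 | 5.4 | 4.5 | 3.0 |
| 0.10: expected reported | 3.0 | 2.7 | 2.25 | 1.5 |
| 0.10: P(at least 2) | 0.82 | 0.77 | 0.67 | 0.45 |

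For the last cell, q = 0.10 × 0.50 = 0.05, and 1 − 0.95^30 − 30 × 0.05 × 0.95^29 = 1 − 0.215 − 0.339 = 0.446. The documents support no particular value of p or w. The table shows only how sensitive a sample of 30 would be.

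**The case against.** The best defense is that 12.1 is a deliberate, narrow exclusion. It requires signs and symptoms to be expected in both intensity and frequency, and an event the investigator attributes to study drug is outside it. Entry excluded creatinine clearance of 60 mL/min or less and hemoglobin of 80 g/L or less (Section 4.3), so acute renal failure or a marked fall in hemoglobin is not an obvious case of an expected intensity. Without a control arm, counting every consequence of the disease as an AE would also inflate the apparent toxicity of the regimen. Progression itself is captured through the response criteria.

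Much of this stands for non-serious events, and it rules out three stronger readings that a reader might infer:
- That 12.1 contradicts 12.2, 12.6.1 and 12.6.2 equally. Only the conflict with 12.6.2 is direct.
- That SAEs may legitimately be withheld under 12.1. A site that did so would breach 12.6.2.
- That toxicity has been shown to be missing from the primary endpoint beyond recovery. The documents show a possible loss, not an actual one, and laboratory-defined events can partly be traced.

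The defense does not resolve the conflict over SAEs. A carve-out prevails over a general rule, but 12.6.2 is itself specific to disease-related events and says the opposite.

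**Conclusion.** The protocol holds two opposing instructions for serious signs and symptoms of myeloma progression, and SAE reporting is still live. This conclusion rests on the text alone and needs no numerical assumption. For non-serious events the finding is weaker. Section 12.1 sits uneasily with 12.2, 12.4.1 and 12.6.1 but can be read as an exception to them, and any loss would lie mainly in clinical events that have no laboratory counterpart. Its size cannot be estimated, and the values in the table are assumptions.

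A reader might infer that 12.1 should be replaced by a rule that records every sign, symptom and laboratory change as an AE. The documents do not support that. Section 12.6.2 speaks only of events that meet the SAE definition. Full AE collection ended with Amendment 7, when the primary analysis was treated as achieved (Synopsis; SAP Section 1), so new wording cannot recover non-serious events already missed.

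**What to change.** 1. Amend Section 12.1 so that it no longer exempts SAEs and refers to 12.6.2. Disease progression is not an SAE term, but signs and symptoms that meet the SAE definition are reported, and the investigator's view that myeloma is the cause goes into the causality assessment. The scale in Section 12.4.2 already allows for an alternative explanation such as concomitant disease.
2. For data already collected, list in the CSR the subjects with treatment-emergent Grade 3 or 4 worsening in hemoglobin, platelets, creatinine or calcium that has no matching AE record, and state which reporting rule sites followed. An unmatched record does not prove that 12.1 was the reason, but it puts an upper limit on the laboratory-defined part of the loss at those grades.
3. Do not reopen non-serious AE collection.

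The cost is a short wording change through the usual amendment route, one listing from data already held and one statement in the report. Reported SAE counts may rise slightly. The change affects reporting only, not treatment.

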12.2. Pre-existing Conditions

In this study, a pre-existing condition (ie, a disorder that was present before the AE reporting period started and noted in the medical history or physical examination eCRF) should not be reported as an AE. If a pre-existing condition worsens during the Treatment Period, the event should then be reported as an AE.

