9. STUDY EVALUATIONS

9.1. Study Procedures by Visit

9.1.1. Overview

The following sections give a brief overview of the Screening Period, Treatment Period, Follow-up Period, and EOT Visit. The Time and Events Schedule summarizes the frequency and timing of safety, efficacy, pharmacokinetic, pharmacodynamic, and other measurements applicable to this study. As of Amendment 8, follow the schedule of events outlined in Table 4 and additional details are provided in Attachment 9.

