11.11. Safety Analyses

The verbatim terms used in the CRF by investigators to identify adverse events will be coded using the Medical Dictionary for Regulatory Activities (MedDRA). All reported adverse events with onset during the treatment phase (ie, treatment-emergent adverse events, and adverse events that have worsened since baseline) will be included in the analysis.

The number and percentage of subjects with treatment-emergent AEs will be summarized according to intensity by using the CTCAE v4.0, drug relationship, and outcome. Laboratory data will be summarized and descriptive statistics will be calculated. Changes in vital sign measurements, physical examination findings, and ECOG performance status will be summarized. Safety laboratory variables will be presented in figures (values versus time) and summarized by value and change from baseline (both absolute and relative).

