2.6.12. Treatment Emergent Adverse Events

Treatment emergent adverse events (TEAEs) are defined as any AE with onset date and time on or after that of the first dose of study drug infusion through 30 days after the last dose of study drug or the day prior to start of subsequent therapy, whichever is earlier; or any AE that is considered related to (probably, or possibly related) study drug regardless of the start date of the event. AEs with missing or partial onset date and time will be considered as treatment-emergent unless the onset date and time of an AE can be determined as earlier than that of the first dose, or later than 30 days after last infusion .

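### Section 12.2 ties reporting of a worsened pre-existing condition to the Treatment Period, which conflicts with the 30-day AE windows in Section 12.6.1 and SAP 2.6.12 and risks inconsistent under-reporting

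*Protocol*

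**What the plan says.** Section 12.2 of the protocol deals with disorders already on record before AE reporting starts. Its default is that they are not AEs. It gives one route back: "If a pre-existing condition worsens during the Treatment Period, the event should then be reported as an AE".

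Three other places set the scope of AE reporting and counting:

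- Protocol 12.4.1, in defining an AE: "This includes any occurrence that is new in onset or aggravated in severity or frequency from the baseline condition". It attaches no Treatment Period limit and points to 12.6.1 for when recording stops.
- Protocol 12.6.1 runs collection from signed consent "until 30 days after the last dose of any component of the treatment regimen", and adds: "All AEs that occur in subjects during the AE reporting period must be reported, whether or not the event is treatment related".
- SAP 2.6.12 counts events as treatment-emergent from the first dose "through 30 days after the last dose of study drug or the day prior to start of subsequent therapy, whichever is earlier". It also counts any event judged related, whatever its start date.

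Protocol 11.11 analyses reported events with onset in the treatment phase, including worsening since baseline, but gives no number of days. Section 9.3 makes the incidence of AEs the primary endpoint.

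**The concern.** A worsening that starts shortly after the last dose falls under two instructions. Section 12.2, the place a site would look for a pre-existing condition, covers only the Treatment Period by name. Sections 12.4.1 and 12.6.1 make the same event an AE that must be reported.

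A site that follows 12.2 could leave the event out, and a site that follows 12.6.1 would enter it. The SAP can count only what was entered, so it cannot repair the difference. The affected quantity is the primary endpoint, in subjects who have just stopped treatment.

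**Working it through.** No figure in the plan needs to be reproduced here. The check is a comparison of windows.

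**Step 1. The windows side by side.**

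| Place | What it covers | Where it ends |
|---|---|---|
| Protocol 12.2 | Worsening of a pre-existing condition | End of the Treatment Period; no date given |
| Protocol 12.4.1 | New onset or aggravation from baseline | No limit of its own; defers to 12.6.1 |
| Protocol 12.6.1 | All AEs | 30 days after the last dose of any component |
| Protocol 11.11 | AEs for analysis, worsening included | End of the treatment phase; no days given |
| SAP 2.6.12 | Treatment-emergent AEs | 30 days after the last dose, or the day before subsequent therapy if earlier |

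**Step 2. Does the Treatment Period end before the 30 days are over?** No passage defines its end, but the usage points that way.

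- Section 9.1.1 names the "Screening Period, Treatment Period, Follow-up Period, and EOT Visit" as separate items.
- Table 3 runs its treatment columns up to discontinuation and puts the EOT visit in a separate column, 3 to 5 weeks after the last dose. That is day 21 to day 35 (3 × 7 and 5 × 7), which straddles the 30-day limit.
- Attachment 8 schedules pregnancy tests in the Treatment Period and, as a separate item, at the EOT visit.
- Section 12.2 itself uses the term AE reporting period one sentence earlier, as does 12.6.1. The Treatment Period is therefore hard to read as a synonym for it.

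**Step 3. A test case.** Take a non-serious worsening of a recorded condition that starts on day 20 after the last dose, before Amendment 7, with no subsequent therapy.

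- Under 12.2, the default of not reporting applies and the stated exception does not reach the event.
- Under 12.4.1 and 12.6.1, it is an AE inside the reporting period and must be reported.
- Under SAP 2.6.12, it counts as treatment-emergent if it was entered.
- A new event on the same day is reported and counted under every section except possibly 11.11, whose window is not defined.

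If subsequent therapy had begun on day 15, 12.6.1 would still require a report. The SAP would then count the event only if it was judged related.

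**Step 4. Size.** The period in dispute is at most 30 days per subject who stops. The documents give no rate of post-dose worsening, so no effect on incidence can be calculated. For scale, one subject among the approximately 30 in Phase 2 is 1/30 = 3.3 percentage points of an incidence. That holds for any missed subject and says nothing about how often this rule causes a miss.

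**The case against.** A reader might infer that 12.2 makes worsening reportable only during treatment, so that every post-dose worsening drops out of the primary endpoint. The documents do not support that. Section 12.2 does not contain the word only. Section 12.4.1 makes aggravation from baseline an AE, and 12.6.1 exempts no pre-existing condition. Tables 1 and 2 schedule AE collection at the follow-up and EOT visits. This is a contradiction, not a defined exclusion.

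A reader might also size the gap by window length: 30/(56 + 30) = 35% for a subject stopping after two 28-day cycles, and 30/(365 + 30) = 8% after a year. These are shares of calendar time, not of events. They assume that the Treatment Period ends at the last dose, and they ignore the SAP's cut-off at subsequent therapy.

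Other limits also stand:

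- A toxicity that led to discontinuation would have begun on treatment and already be an AE.
- Expected deterioration due to myeloma is kept out of AE reporting by 12.1, whatever 12.2 says. This can apply to anaemia and renal insufficiency, which Section 1.1.1 lists among the findings of the disease.
- From Amendment 7 only SAEs are collected, and under Amendment 8 only SAEs and second primary malignancies. Editing 12.2 now cannot add non-serious events.

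What the objection does not remove is the conflict itself. The section written for pre-existing conditions gives a different window from the section that governs reporting. It also makes no distinction by seriousness. Section 12.6.2 separately requires serious events to be reported, but 12.2 still bears on whether a worsening is treated as an AE at all, and serious events are still collected.

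**Conclusion.** Wrong as written (minor). Section 12.2 is not aligned with 12.4.1, 12.6.1 and SAP 2.6.12 for a worsening that begins after the Treatment Period and within 30 days of the last dose. Sites may therefore report the same event differently, and AE incidence may be undercounted. The direction is towards too few events; the amount is unknown.

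The conclusion rests on reading the Treatment Period as closing before the EOT visit, which the documents imply but do not define. The consequence is limited. The endpoint is descriptive, with no hypothesis test (SAP 1.3). The non-serious part concerns data gathered before Amendment 7, which are the data behind the primary analysis. Serious worsening has its own reporting route in 12.6.2.

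**What to change.** - In Protocol 12.2, replace *during the Treatment Period* with *during the AE reporting period (Section 12.6.1)*. A cross-reference is better than a newly written window. It carries over the start at signed consent, the 12.6.1 rule that sends non-serious events before first dose to medical history, and the end at 30 days. The cut-off at subsequent therapy stays where it belongs, as an analysis rule in the SAP.
- In Protocol 11.11, define *treatment phase* as the treatment-emergent window of SAP 2.6.12.
- In the study report, state that post-dose worsening of pre-existing conditions may be under-reported in the data collected before Amendment 7.

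The cost is a few words in two protocol sections, a short reminder to sites and one sentence in the report. The edit will not recover non-serious events that were never entered, so the disclosure is needed as well.
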